
of life. Beginning the management of clubfoot in early infants is technically less challenging due to childrens' rapid growth as well as easy tissue manipulation ^[15].

Reports on the failures of the Ponseti method have shown that the non-compliance with the bracing regimen following Ponseti casting is the primary reason for relapse ^[16]. Relapse or reoccurrence is defined as the reappearance of any of the components of the deformity including midfoot cavus, forefoot adductus, hindfoot varus and ankle equinus positioning of the foot ^[9,11]. A study done by Dobbs et al. 2004 showed that individuals who were non-compliant with their bracing were 183 times more likely to relapse. Previous literature reported that relapse rates between 10-30% are common^[17]. Of these relapses it is estimated that 78% of all relapses occur due to non-compliance with bracing, whereas only 7% of relapses occur with full compliance^[17]. Thus, it is critical that bracing regimens be followed strictly and consistently. One of the ways that this can be addressed is through improving brace design for comfort and long-term wear. Some of the most problematic causes for non-compliance with bracing are skin lesions such as blistering, sleeping problems from discomfort, parental concerns about the restrictiveness of leg movement in the brace, and dislodgment of the foot from the brace due to kicking ^[14,17,18]. In recent years the focus for the improvement of outcomes of CTEV following Ponseti casting has focused on the production of a brace that leads to higher compliance rates and therefore better treatment outcomes by addressing these four main problems with FAB. A few studies have reported increased compliance with reduced rates of relapse when adapting the bracing methodology via improving the standard rigid bar to be more dynamic ^[14,19]. In addition, Chen et al. 2007 created custom AFOs that they fastened to an articulating bar and found success in decreasing skin blistering (3.6% of patients in compared with 22% with traditional FAB) and non-compliance rates (7.2% compared to 42% with traditional FAB) as reported by parents. The AFO made by [name] was made of one-eighth-inch plastic copolymer physically molded to the patient's foot. A custom Duraflex liner was then inserted into the plastic molded piece and attached to an articulation bar. However, one drawback of their custom orthoses is that the average cost for the custom bracing was nearly 4 times that of the traditional brace ^[17]. Our orthoses would be more beneficial because it allows for the use and improvement of the already widely used Mitchell shoes, a much more cost-effective option. In addition, our orthoses are different in that the feet are scanned in 3D and edited in CAD before the inserts will be 3D printed. In general, most studies have focused on the feet are implementation of dynamic bars that allow greater range of motion ^[14,19]. The standard for the Ponseti brace is maintenance of the completely corrected foot in 60-70 degrees of external rotation on the affected side and in 30-40 degrees of external rotation on the normal side. The bar should be bent 5-10 degrees with the convexity pointing away from the child to hold the feet in a valgus position. The feet should be placed on the bar so that the heels of the shoes are at shoulder width ^[11]. Knees are left free so the child can kick straight and stretch the Achilles tendon. It is also important to note that compliance rates are almost always overestimated when being reported through parental survey and thus we will be assessing compliance rates using heat sensors inserted into the back of the insert orthotics in order to get a more accurate reading of time spent in the bracing apparatus ^[20]. The use of these sensors is new to research on bracing compliance for clubfoot and would be one of the first extremely reliable measures of parental compliance. Our custom orthotics should correct for the slipping of the infant's foot out of the Mitchell shoes as well as decreasing the number of skin lesions from rubbing on the leather shoe, thus increasing compliance and overall functional outcomes.

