
D. DESIGN AND METHODS

Patients will be recruited by [name] during normal clinic hours by asking existing patients if they would be willing to participate in our small study attempting to improve aspects of the bracing process. . . Patients will be randomized as they are recruited via coin flip until we have 5 spots filled in one group then assign all others to ensure 5 patients with the FO + Mitchell shoes and 5 patients with just the Mitchell shoes. Customized orthotic group will receive a customized AFOs inserted into Mitchell shoes; "Mitchell" groups will receive standard Mitchell shoes only. Inclusion criteria are as follows: less than 12 months old (no age minimum), no neuromuscular disease involved, treated by Ponseti casting, idiopathic bilateral or unilateral clubfoot, no other congenital foot deformity, and no previous open surgeries to treat the deformity. Exclusion characteristics for this study include: patients with prior surgical treatment, not treated by Ponseti casting, an underlying syndrome, or neurological disorder.

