We will be aiming to have 10 individuals in our preliminary trial before we move on to trying this method with larger cohorts. These numbers will allow us to run a power analysis to determine the number of individuals needed for a follow up study to confirm or refute any results we have found.

F. DRUGS OR PROCEDURES (may attach activity table if available - lab draws, EKG, chest x-rah, surgery, genetics, survey)

The participants will be scanned from the tibia to the tip of the toes by the Milwaukee Topographic system which consists of a handheld wand and sensors as well as spinal metrics. There will be a parental survey as a part of the research design. Manipulation of the foot via a trained individual will occur in order to assess the functionality and degree of deformity of the infant foot as we cannot assess gait at this early stage.

G. RISK CATEGORY:

X (1) [**45 CFR 46.404**](#) - Research not involving greater than minimal risk to the children.

(2) [**45 CFR 46.405**](#) - Research involving greater than minimal risk but presenting the prospect of direct benefit to the individual child subjects involved in the research.

(3) [**45 CFR 46.406**](#) - Research involving greater than minimal risk and no prospect of direct benefit to the individual child subjects involved in the research, but likely to yield generalizable knowledge about the subject's disorder or condition.

(4) [**45 CFR 46.407**](#) - Research that the IRB believes does not meet the conditions of 45 CFR 46.404, 46.405, or 46.406, but finds that the research presents a reasonable opportunity to further the understanding, prevention, or alleviation of a serious problem affecting the health or welfare of children.

H. RISKS AND THE PRECAUTIONS WHICH WILL BE TAKEN TO MINIMIZE RISK EXPOSURE

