The current research and orthotic implementation may decrease the risk of clubfoot relapse and it may provide a greater level of comfort for the child throughout the bracing process. It may also allow for the use of traditional Mitchell shoes in infants with especially small and malformed feet. Specifically it may reduce the incidence of heel slippage and thus lead to a longer wear time and lower likelihood of relapse.

L. STOPPING POINTS THAT WOULD NOT ALLOW THE STUDY TO CONTINUE AS PROPOSED

Any parent who objects to their child wearing the brace will be removed from the study at their wish. If parents of the children wish to only participate in the traditional bracing protocol their wish will be respected and will not be included in either of the study cohorts.

M. IS THERE A DATA SAFETY MONITORING BOARD IN PLACE? WHO ARE IT'S MEMBERS? HOW OFTEN DO THEY MEET?

There is no safety monitoring board in place for this study.

N. DESCRIBE HOW THE CONSENT AND ASSENT PROCESS WILL TAKE PLACE. INCLUDE A LIST OF APPROPRIATELY TRAINED PERSONNEL WHO WILL BE INVOLVED.

Investigators will receive consent from all parents and answer all questions. We are requesting a waiver of assent for study because the children participants will be less than 12 months old and thus will be unable to assent.

O. PROCEDURES TO BE EMPLOYED IN ANALYZING DATA AND THE ANTICIPATED SIGNIFICANCE OF THE PROPOSED STUDY

A power analysis will be performed to determine the exact number of patients needed for future study. We will be aiming to have 10 individuals in a preliminary trial run and then move on to larger cohort studies. In children with bilateral clubfoot, each foot will be used as an independent observation in the statistical analysis. Means will be compared using Student's t-test. Statistical significance will be considered at a two-tailed level of < 0.05 .

P. FINANCIAL RELATIONSHIPS

There are no financial partnerships implicated in this study. This research is funded by the Department of Orthopaedic Surgery.

Q. ADVERTISEMENTS / FLIERS

No fliers or advertisements will be used.

R. BIBLIOGRAPHY

- ¹ Azarpira MR, Emami MJ, Vosoughi AR, Rahbari K. Factors associated with recurrence of clubfoot treated by the Ponseti method. *World J Clin Cases*. 2016;4:318.
- ² Radler BC, Manner HM, Suda R. Radiographic Evaluation of Idiopathic Clubfeet. 2007;1177-1183.
- ³ Wynne-Davies R. Family Study and The Cause of Clubfoot. *J Bone Jt Surg*. 1964;46:445-463.

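### Section O's only criterion for a between-arm difference is p < 0.05, with no interval planned; in a 5 v 5 sizing pilot, report child-level estimates with 95% CIs and draw no efficacy verdict

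*Combined protocol and SAP*

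**What the plan says.** - **Analysis (section O).** "Means will be compared using Student's t-test", and then "Statistical significance will be considered at a two-tailed level of < 0.05". Neither this section nor any other plans an effect estimate with a confidence interval, or says how a non-significant result is to be read.
- **Size (section D).** Allocation continues until there are "5 patients with the FO + Mitchell shoes and 5 patients with just the Mitchell shoes".
- **Purpose (section E).** "These numbers will allow us to run a power analysis to determine the number of individuals needed for a follow up study"; that later study is then "to confirm or refute any results we have found". Section O also opens with the planned power analysis. No power, expected difference or SD is stated for the pilot itself.
- **Hypothesis (section B).** It is directional: better compliance, better function and fewer relapses with the insert.
- **Benefit cited (section C).** A published custom orthosis had "non-compliance rates (7.2% compared to 42% with traditional FAB) as reported by parents". This trial measures wear with one temperature logger per child.

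**The concern.** A study meant to size another study needs estimates and a statement of how uncertain they are. Section O instead supplies a yes/no rule, and it is the only stated criterion for calling the arms different. With five children per arm that rule says little about whether the insert works. A non-significant result is the likely outcome for a wide range of real benefits and could be read as no benefit. A significant result, if the true effect is small or moderate, will tend to overstate it. Both problems arise for a single outcome tested once at child level, so they are separate from multiplicity.

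**Working it through.** The sample size of 10 is stated without inputs, so there is no power figure to reproduce. The check asks what the p < 0.05 rule does with 5 v 5 children.

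**Inputs from the documents.** n = 5 per arm (section D); two-sided 0.05 and Student's t-test (section O); 42% v 7.2%, a difference of 34.8 points (section C).

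**Assumption.** The documents give no SD for wear time, so a range of 0.5 to 2.0 SD is used.

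**1. Threshold for a mean difference.** The critical t on 8 df is 2.306. Significance needs an observed difference above 2.306 × √(2/5) = 1.46 observed SD. The 95% CI half-width is the same 1.46 observed SD.

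**2. Yes/no non-compliance at the cited rates.** Let X be the number non-compliant out of 5 at 42%, and Y the number out of 5 at 7.2%.
- P(X = 3, 4, 5) = 0.2492, 0.0902, 0.0131
- P(Y = 0, 1, 2) = 0.6882, 0.2670, 0.0414

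*t-test on 0/1 data.* In the expected direction the significant tables are 3, 4 or 5 v 0, 5 v 1 and 5 v 2. For example, 3 v 0 gives t = 0.6/√(0.15 × 0.4) = 2.45, which is significant; 4 v 1 gives 0.6/√(0.20 × 0.4) = 2.12, which is not. The smallest significant gap is 60 points.

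Power = (0.2492 + 0.0902 + 0.0131) × 0.6882 + 0.0131 × (0.2670 + 0.0414) = 0.2466. Adding 0.0002 for the opposite direction gives **24.7%**.

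*Fisher's exact test.* The significant tables are 4 or 5 v 0 and 5 v 1. The smallest significant gap is 80 points.

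Power = (0.0902 + 0.0131) × 0.6882 + 0.0131 × 0.2670 = **7.5%**; the opposite direction adds a negligible amount.

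A significant yes/no result would therefore overstate the cited difference by at least 60/34.8 = 1.7 times (t-test) or 80/34.8 = 2.3 times (Fisher).

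**3. Continuous outcome such as wear time.** Power is from the noncentral t with 8 df and noncentrality d × √(5/2). The other columns are from 400,000 simulated trials per row. Exaggeration is the mean absolute raw difference among significant results, divided by the true difference.

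| True effect (SD) | Power | Mean exaggeration if significant | Significant estimates below the truth |
|---|---|---|---|
| 0.5 | 11% | 2.9 | 0.1% |
| 0.8 | 20% | 2.0 | 1% |
| 1.0 | 29% | 1.7 | 4% |
| 1.26 | 42% | 1.4 | 11% |
| 1.5 | 55% | 1.3 | 20% |
| 2.0 | 79% | 1.1 | 38% |

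The 1.26 row is the cited 42% v 7.2% placed on a probit scale, which is itself an assumption. Power of 50% needs a true effect of 1.41 SD, and 80% needs 2.02 SD.

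**4. What an interval would show.** If 2/5 v 0/5 were non-compliant, the difference is 40 points with a 95% CI (Newcombe) of about −12 to +77. The 95% CI for an SD estimated on 8 df runs from 0.68 to 1.92 times the estimate. The follow-up power analysis would inherit both uncertainties.

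**The case against.** The case against has force on five points.

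- **The test is not the only use of the data.** The power analysis is the pilot's stated purpose, and the plan never claims adequate power. This stands: p < 0.05 is the only stated criterion for a difference, not the only planned output.
- **No decision hangs on significance.** A reader might infer that a non-significant result would end the device, or that an inflated estimate would be fed into the follow-up study. The documents do not support either. Moving on to larger cohorts is not made conditional on p < 0.05, and nothing says the power analysis will use only significant estimates; without that selection the mean difference is not inflated.
- **The cited rates are a weak benchmark.** They come from another orthosis on an articulating bar and are parent-reported. This trial logs time in the brace and defines no compliance cut-off, and Fisher's test is not in the plan. So 7.5% should not be quoted without the 24.7% from the test that is planned.
- **Exaggeration is not universal.** A reader might infer that every significant result must be greatly inflated. For means this is false: the 1.46 threshold is in observed SDs, so a small sample SD can give significance with a raw difference below the truth, as the last column of the table shows.
- **Intervals and t-tests agree.** For a mean difference the 95% CI excludes zero exactly when p < 0.05, so an interval adds no precision. This too stands. The gain lies in showing the imprecision and in not drawing a verdict.

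A further objection is that section O says "each foot will be used as an independent observation in the statistical analysis", so foot-level outcomes such as the Dimeglio score could be tested on up to 10 v 10 feet. That does not rescue the rule. Wear is logged once per child, and the extra power for foot-level outcomes comes from treating correlated feet as independent, which is a separate issue.

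**Conclusion.** The point holds in a limited form. Section O judges differences by p < 0.05 alone and plans no interval, which does not suit a pilot whose purpose is sizing. At the one quantified compliance benefit in the protocol, a non-significant result is about 75% likely with the planned t-test on yes/no data and about 92% likely with Fisher's test. For wear time the answer depends on an SD the documents do not give: non-significance is the likelier result below a true effect of about 1.4 SD. Large exaggeration is confined to yes/no outcomes at the cited rates and to small or moderate continuous effects, and has largely gone by 2 SD. This is a cheap improvement to what the trial may conclude. It does not show that the trial is invalid or should be larger.

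**What to change.** Replace the significance sentence in section O with:

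> Between-arm differences are reported per child as the mean difference with 95% CI (for yes/no outcomes, counts with exact CI). P-values, if shown, are descriptive, and no conclusion that the insert does or does not improve an outcome is drawn from this trial. The power analysis for the follow-up study uses these estimates with their uncertainty, whether or not they are significant.

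Rewording section E, so that the follow-up study tests the hypothesis rather than confirming or refuting pilot results, is optional because that section already treats the pilot as provisional.

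The change needs no extra children, visits or data. Its cost is the option to announce a significant result from the pilot.

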Children's Hospital
and Health System™

**INSTITUTIONAL REVIEW BOARD
SUMMARY**

Customized Orthosis for Children with Clubfoot Following Ponseti Casting

NCT03853811

January 17, 2019

PRINCIPAL INVESTIGATOR: [name]

STUDY TITLE: Customized Orthosis for Children with Clubfoot Following Ponseti Casting

A. PURPOSE OF THE STUDY

The purpose of this study will be to design a novel customized Ankle Foot Orthosis (AFO) using 3D topographic scanner and CAD/CAM based technology then:

1. Determine differences of the patient compliance by recording the time in the brace and comparing between customized AFO and traditional straight-last shoes
2. Compare changes of foot and ankle alignments between customized AFO and traditional Mitchell shoes
3. Evaluate changes of functional outcomes between the two groups in a follow-up

B. HYPOTHESIS / SPECIFIC AIMS

We hypothesize that following Ponseti casting, the implementation of customized ankle foot orthotics (AFO) with Ponseti bracing will improve patient compliance and functional outcomes as well as lead to fewer relapses in comparison to the standard bracing with Mitchell shoes.

C. BACKGROUND, SIGNIFICANCE, AND RATIONALE

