
Table 1. Table of tasks to be performed at each clinical visit from the beginning of intervention to the end of the study period. Gray colored boxes indicate the task will be performed.

Task	Last Brace Removed	2 Week Follow Up	12 Week Follow Up	24 Week Follow Up
Check Foot				
Measure Dimeglio Score				
Scan Foot (Milwaukee Topographic System)				
Initial Survey				
Follow up Survey				
Transfer Data from Sensor				
Assess Fit and Adjust Orthotics as Needed				

Analysis of clubfoot functional outcomes will be assessed using Dimeglio Scores before and after Ponseti Casting as well as after 2, 12, and 24 weeks of bracing. Dimeglio scores are often used to assess the severity of clubfoot deformities and will give us a baseline as well as a level of improvement after casting and bracing. Dimeglio scores have been shown to provide good prognostic significance ^[5]. Other clinical parameters that we will be recording are: unilateral or bilateral CTEV, any surgeries performed (ex. achilles tenotomy, anterior tibial transfer, soft tissue release), level of brace adherence as reported by sensor, number of relapses, number of Ponseti casts needed to achieve correction, passive end dorsiflexion and abduction angles, and instances of rocker bottom deformity. The sensor to detect the body temperature will be embedded inside of the AFO and data will be stored in the sensors for three months. At follow up, the data will then be transferred to and saved to the computer via Bluetooth. In addition to these parameters we will use a parental questionnaire recording the following: occurrences of skin lesions, age of treatment initiation, age at each follow up, sex of child, prior treatments, family history of CTEV, parental marital status, insurance type, highest educational level achieved by parents, yearly family income, brace adherence as reported by parents, and reported of instances of foot slipping out of brace as well as any reasons for decreased compliance. Investigators will review the survey during clinical visits and will be able to address parent's concerns at that time. We are collecting data on these socioeconomic factors in order to help identify groups that may need additional attention or interventions in order to help reduce disparities in outcomes. Images of the child's feet in the orthotic or bracing device may be taken.

E. TOTAL NUMBER OF HUMAN RESEARCH PARTICIPANTS PROPOSED FOR THIS STUDY AT THIS SITE AND GLOBALLY. WHAT ARE THESE NUMBERS BASED ON?

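### One 0.05 threshold with no primary outcome, no primary time point and no outcome named for sizing the follow-up study: roughly a 20% to 37% chance of a false positive if about nine listed outcomes are each tested once

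*Combined protocol and SAP*

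**What the plan says.** All references are to the combined protocol and SAP.

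- **Section O** holds the whole analysis plan for between-arm comparisons: "Means will be compared using Student's t-test", and then "Statistical significance will be considered at a two-tailed level of < 0.05". Neither sentence is tied to an outcome or a visit.
- **Section B** hypothesises that the orthosis "will improve patient compliance and functional outcomes as well as lead to fewer relapses". The three domains stand side by side and none is called primary. Section A lists time in the brace first among three purposes, also without calling it primary.
- **Section D** says function "will be assessed using Dimeglio Scores before and after Ponseti Casting as well as after 2, 12, and 24 weeks of bracing". A further list opens with "Other clinical parameters that we will be recording are", and a parental questionnaire follows. Together they give about nine outcomes that could be compared between arms: Dimeglio score, sensor-measured wear, parent-reported wear, relapses, dorsiflexion angle, abduction angle, rocker bottom deformity, skin lesions and the foot slipping out. Surgeries would be a tenth.
- **Section D** also sets the allocation, to "ensure 5 patients with the FO + Mitchell shoes and 5 patients with just the Mitchell shoes".
- **Section E** gives the purpose: "We will be aiming to have 10 individuals in our preliminary trial before we move on to trying this method with larger cohorts". The results feed a power analysis for a follow-up study "to confirm or refute any results we have found". Neither section E nor section O says which outcome that power analysis will use.

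**The concern.** A threshold with no stated scope lets any comparison below 0.05 be called significant. With several candidate outcomes and no primary, the chance of at least one such result is well above 5% even if the orthosis has no effect.

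The larger stake is the study's own stated use. A power analysis needs one outcome and an assumed effect. If the outcome is picked after the data are seen, the one with the largest difference is the natural candidate, and with five children per arm that difference is mostly noise. The follow-up study could then be too small and aimed at the wrong endpoint.

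**Working it through.** The plan states no familywise error rate, and the sample size of 10 has no power, effect size or standard deviation behind it. There is therefore no figure of the plan's to reproduce.

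**Inputs from the documents.** Two-sided 0.05 and Student's t-test (section O); 5 v 5 children and nine candidate outcomes (section D); three hypothesised domains (section B).

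**Assumptions, not in the documents.** No true effect; one test per outcome; equal correlation between outcomes, varied from 0 to 0.7; children, not feet, as the unit.

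**Step 1. Independent outcomes.** The chance of at least one p<0.05 in k tests is 1 − 0.95^k.
- k = 9: 1 − 0.95^9 = 0.370
- k = 3: 1 − 0.95^3 = 0.143

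**Step 2. Rare events.** Four of the nine (relapse, rocker bottom, skin lesions, slippage) are events or counts. Exact enumeration of the t-test at 5 v 5 gives a false-positive rate of 0.2% at a 5% event rate, 1.0% at 10%, 3.8% at 20% and 4.4% at 22%. Take five continuous outcomes plus four binary ones at these assumed rates. If independent, the total is 1 − 0.95^5 × 0.998 × 0.990 × 0.962 × 0.956 = about 0.30.

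**Step 3. Correlated outcomes.** Simulation of 5 v 5 t-tests (100,000 runs per cell), with binary outcomes made by cutting correlated normal variables at the rates above:

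| Correlation | Nine continuous | Five continuous, four binary | Three continuous |
|---|---|---|---|
| 0 | 37% | 30% | 14.3% |
| 0.5 | 29% | 25% | 12.9% |
| 0.6 | 26% | 23% | 12.3% |
| 0.7 | 22% | 21% | 11.4% |

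(The zero-correlation row is from the formulas.)

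Relapse is itself an event. With two continuous domains and relapse as a binary outcome, all independent, a 10% relapse rate gives 1 − 0.95² × 0.990 = 10.7%, and a 20% rate gives 1 − 0.95² × 0.962 = 13.2%. Section C cites relapse rates of 10% to 30%.

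**Step 4. Size of the best-looking null effect.** In the same simulation, the median of the largest absolute standardised difference among nine null continuous outcomes is 1.30 at correlation 0, 1.15 at 0.5 and 1.01 at 0.7. For one outcome fixed in advance the median is 0.44.

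**Step 5. What that does to the follow-up.** Assume 80% power and two-sided 0.05. The number per arm is 2(1.96 + 0.84)²/d² = 15.7/d².
- d = 1.30: 9.3, so 10 per arm
- d = 1.15: 11.9, so 12 per arm
- d = 1.01: 15.4, so 16 per arm

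Each would be a study planned around an effect that is not there. At 5 v 5, p<0.05 needs an observed difference of 2.306 × √(2/5) = 1.46, so an outcome could be selected in this way without having reached significance.

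**The case against.** The strongest reply is that section O does not say every outcome will be tested. It names a test and a threshold, and section D's list is of data to be recorded. A reader might infer that every outcome and visit is judged at 0.05. That follows from a rule with no stated scope, but the documents do not say it. This stands, and it is why the figures above are conditional. Restricting the tests to the three hypothesised domains shrinks the problem without removing it.

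A reader might go further and count nine outcomes at three visits, 27 tests, for 1 − 0.95^27 = 75%. The documents do not support that. The 2, 12 and 24 week schedule is stated only for the Dimeglio score, the shading of Table 1 cannot be read in the available text, and repeated measurements on one child are not independent.

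The high end of the range also needs nine continuous, uncorrelated outcomes. Sensor-measured and parent-reported wear describe the same behaviour, and the two angles describe the same foot, so some pairs may be strongly correlated. At a correlation of 0.9 nine continuous tests give 13.5%. Hence the wide range.

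Finally, this is a preliminary trial whose findings are to be confirmed or refuted. That limits the harm of a single chance result. It does not answer the sizing problem, because sizing the next study is what the pilot is for. Nor do the documents say that the best-looking outcome will be chosen. They leave it possible.

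**Conclusion.** The gap is real and should be closed. The plan has one threshold of unstated scope, no primary outcome or time point, and no named outcome for the follow-up power analysis.

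If nine outcomes were each tested once with no true effect, the chance of at least one p<0.05 would be roughly 20% to 37% for correlations of 0 to 0.7 and up to four rare-event outcomes at assumed rates of 5% to 22%. For the three hypothesised domains, treated as continuous, it is about 12% to 14% at correlations of 0 to 0.6, more than twice the nominal 5%. It falls towards 10% if relapse is rare or the correlation is stronger.

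All these figures count children. Section O counts each foot of a bilateral case as independent. That is a separate issue and pushes the other way: with all children bilateral and an assumed within-child correlation of 0.5, a single foot-level test has a true error of about 12%.

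**What to change.** Add a paragraph to section O, for example:

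*Sensor-measured wear over 24 weeks, summarised as one value per child, is the single primary outcome. It is the only outcome tested at two-sided 0.05, and it is the outcome used for the follow-up power analysis. All other outcomes and visits are exploratory and are reported as between-arm differences with 95% confidence intervals, without claims of significance.*

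The choice follows the plan's own reasoning. Time in the brace is the first purpose in section A, section C prefers sensors because parents tend to overstate wear, and section D provides a sensor for each of the 10 children. One value per child also keeps the primary test clear of the rule that counts feet as independent. The wording should define the summary and its start date, since section D has all children in Mitchell shoes alone for about a week while the orthosis is made.

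The cost is one paragraph and no new data. The primary test's error returns to 5%. The downside is that no significance claim can be made for secondary outcomes, including Dimeglio score and relapse. If the sponsor prefers to keep nine tests, a Bonferroni threshold of 0.05/9 = 0.0056 holds the overall error to at most 5%, but that would still leave the sizing outcome to be named.
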